#### **11.5** Summary of Efficacy Analyses

Endpoint	Analysis	Populations
Change from baseline (Visit 1) to day 98 (Visit 4) of the skin hydration	Paired Student's t-test/ Wilcoxon signed-rank test	FAS PP
Change from baseline (Visit 1) to day 21 (Visit 2) of the skin hydration	Paired Student's t-test/ Wilcoxon signed-rank test	FAS

CONFIDENTIAL Page 13 of 23

Statistical Analysis Plan Version no. 1.0 – 20/03/2023 Clinical Investigation Plan Code FOLIAGE - 2022 EudraCT number NA

Change from baseline (Visit 1) to day 42 (Visit 3) of the skin hydration	Paired Student's t-test/ Wilcoxon signed-rank test	FAS
Percentage of subjects improved (Responders) on skin hydration at Day 98 (Visit 4) in comparison to the baseline visit	Number (N) and the proportion of subjects (%) for each item	FAS
Percentage of subjects improved (Responders) on Investigator's Evaluation of skin texture, skin tone, smoothing of the fine lines and wrinkles at each time point (Visit 2, Visit 3 and Visit 4) in comparison to the baseline visit	Number (N) and the proportion of subjects (%) for each item	FAS
Percentage of subjects improved on the Global Aesthetic Improvement Scale (GAIS) at each time point (Visit 2, Visit 3 and Visit 4) in comparison to the baseline visit	Number (N) and the proportion of subjects (%) for each item	FAS
Percentage of subjects improved on the Patient's Aesthetic Improvement Scale (PAIS) at each time point (Visit 2, Visit 3 and Visit 4) in comparison to the baseline visit	Number (N) and the proportion of subjects (%) for each item	FAS
Subject's Evaluation of satisfaction with the treatment at Day 98 (Visit 4) by means of a 5-items scale	Number (N) and the proportion of subjects (%) for each item	FAS

#### 12. SAFETY EVALUATION

#### **12.1** Extent of Exposure

The extent of exposure is 42 ( $\pm$  4) days.

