7.1 Sample Size Determination

Assuming an average difference in the skin hydration evaluated through corneometer skin examination (capacitance) between baseline and Day 98 of 7.5, with a standard deviation of 8, 20 subjects will allow to appreciate this difference as statistically significant at an alpha = 0.05 and a 95% power. Considering the above and a possible drop-out rate of 20%, 24 subjects will be recruited.

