16.1 Study Discontinuation

Subjects may be discontinued at any time from the study for any of the following reasons:

- An AE occurs that, in the opinion of the Investigator, makes it unsafe for the subject to continue in the study
- Lack of compliance of the subject to the study treatment or assessments
- The subject needs to use a medication/treatment not allowed
- The subject is lost to follow-up
- > The subject dies
- The subject withdraws consent

CONFIDENTIAL Page 40 of 51

- The Investigator, for any reason, terminates the entire study, or terminates the study for that subject or the attending physician requests that the subject be withdrawn for any medical reason
- The Sponsor or the Regulatory Authority or the Ethics Committee, for any reason, terminates the entire study or terminates the study for this site or for a particular subject.

If a subject is discontinued from the study, the Investigator will, as far as possible, complete the end of study visit (Visit 4) e-CRF fields. The Investigator should try to ascertain the reason(s) for withdrawal, while fully respecting the subject's rights.

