#### 7. SAMPLE SIZE AND STATISTICAL POWER CONSIDERATION

It was assumed an average difference in the skin hydration evaluated through corneometer skin examination (capacitance) between baseline and Day 98 of 7.5, with a standard deviation of 8. With a statistically significant difference at an alpha = 0.05 a sample size of 20 subjects had 95% power to detect the above estimated difference Considering the above and a possible drop-out rate of 20%, 24 subjects have been recruited.

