## **8.3** Safety Population

The Safety analysis set (SAF) population will include all subjects enrolled who sign informed consent and receive at least one administration of the investigational device.

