#### **9.1.2** Duration of Exposure

The three-injection treatment session were scheduled at Visit 1 (Day 1), Visit 2 (Day 21  $\pm 4$  days) and Visit 3 (42  $\pm 4$  days). A Follow up visit (Visit 4) was scheduled at days 98  $\pm 7$  days.

The extent of exposure will be estimated based on the treatment duration.

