#### 10. STUDY SUBJECTS

#### **10.1** Disposition of Subjects

Subjects' disposition by study visit will be described and summarized in the Table 1.1. Reasons for withdrawal will be described.

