#### **10.2** Protocol Deviations

Protocol deviations will be reviewed and discussed with the sponsor before the database lock. Statisticians and DM will also review protocol deviations in order to define the database lock.

Protocol deviations will be described in the Table 1.2 and in the Listing 2.

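### Minor: SAP 12.1 fixes the extent of exposure at the scheduled 42 (±4) days, and no listed table reports the sessions actually received

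*SAP*

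**What the plan says.** SAP 12.1 consists of one statement: "The extent of exposure is 42" (±4) days. It names no population and refers to no table.

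SAP 9.1.2 sets out the schedule (injections at Day 1, Day 21 ±4 and Day 42 ±4, follow-up at Day 98 ±7) and adds: "The extent of exposure will be estimated based on the treatment duration". It gives no per-subject rule and does not say whether the duration is the actual or the scheduled one.

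The SAF takes subjects who sign consent and "receive at least one administration of the investigational device" (SAP 8.3). Protocol 16.1 allows early stopping: "Subjects may be discontinued at any time from the study for any of the following reasons". Protocol 7.1 allows for a "possible drop-out rate of 20%, 24 subjects will be recruited", and SAP 7 says "a sample size of 20 subjects had 95% power to detect the above estimated difference".

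Two parts of the plan come close to exposure. On disposition, SAP 10.1 has "disposition by study visit will be described and summarized in the Table 1.1". On deviations, SAP 10.2 has "Protocol deviations will be described in the Table 1.2 and in the Listing 2". SAP 9.1.3 and 11.3 declare treatment compliance not applicable. The safety tables in SAP 14.3 are 3.1 and 3.2, both on adverse events, and the listings in SAP 16.2 include none for exposure.

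**The concern.** An analysis plan should say how exposure will be measured. SAP 12.1 gives the answer in advance, taken from the visit schedule. Anyone treated once is in the SAF and subjects may stop at any time, so the set can contain people with one or two sessions. For them the printed duration would be wrong.

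The consequence is one of safety reporting. SAP 12.2 reports total event counts as well as the proportion of subjects with an event, and Protocol 6.4.1 has local and systemic events recorded after each session. The expected effects are mainly pain, erythema, edema and bruising from the injections. A reader interpreting a total event count would want to know how many sessions produced it, and no listed table gives that number.

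**Working it through.** **Inputs.** Sessions at Day 1, Day 21 ±4 and Day 42 ±4 (SAP 9.1.2; Protocol Table 1). 24 recruited to keep 20 (Protocol 7.1; SAP 7). Neither document gives the timing of drop-out or a formula for exposure. I assume: exposure = day of last session received − day of first session + 1.

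**The plan's figure.** Three sessions: 42 − 1 + 1 = 42 days, with a window of 38 to 46. This reproduces 42 (±4), so the figure is the scheduled duration for a subject who completes all three sessions in window.

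**Other members of the SAF.**
- Two sessions: 21 − 1 + 1 = 21 days, window 17 to 25.
- One session: 1 − 1 + 1 = 1 day.

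**Effect on the SAF mean.** Planned loss: 24 − 20 = 4.

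| All 4 leave after | Mean days over 24 | Total sessions |
|---|---|---|
| session 3 | 24×42/24 = 42.0 | 3×24 = 72 |
| session 2 | (20×42 + 4×21)/24 = 924/24 = 38.5 | 72 − 4 = 68 |
| session 1 | (20×42 + 4×1)/24 = 844/24 = 35.2 | 72 − 8 = 64 |

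A loss of 4 from 24 is 16.7%. The stated 20% would be 0.20 × 24 = 4.8 subjects. With 5 lost, the means are (19×42 + 5×21)/24 = 37.6 days after session 2 and (19×42 + 5×1)/24 = 33.5 days after session 1.

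**Even drop-out over Days 1 to 98 (assumption), 4 lost.** After session 1 only: 4×20/97 = 0.82 subjects. After session 2 only: 4×21/97 = 0.87. Together, 1.69 subjects miss a session. Mean: (22.31×42 + 0.82×1 + 0.87×21)/24 = 39.8 days. Sessions: 72 − 2×0.82 − 0.87 = 69.5.

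**Whether another section supplies actual exposure.**
- Table 1.1 shows disposition by visit, and attending a visit is not the same as being injected. A subject who stops early is still to complete a Visit 4 (Protocol 6.4.1 and 16.1), so a Visit 4 record does not show that session 3 was given.
- Table 1.2 and Listing 2 (deviations) and Listing 1 (discontinued subjects) allow partial inference, subject by subject.
- SAP 14 permits additional tables but commits to none on exposure.

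**The case against.** The strongest reply is that SAP 9.1.2 is the operative rule. It speaks of estimating exposure from treatment duration, and a scheduled duration needs no estimating, so actual duration is the natural reading and 12.1 merely gives the nominal course length. That reading is possible, and it means the two sections cannot be called contradictory. The text does not require it, however, and 12.1 taken with 9.1.2 supports the scheduled reading just as well.

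The second reply is that most of the information is already planned. There is one session per treatment visit, so disposition by visit approximates the session count, and Listings 5.1 and 5.2 show per-subject data at each visit. This narrows the gap without closing it: the measurements at Visits 2 and 3 precede the injection, and none of these outputs counts sessions given.

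The third reply is that the size is hypothetical, and this stands. The 20% is a sample-size allowance. A reader might infer from it that 4 or 5 subjects will miss sessions, but the documents do not say so: 98 − 42 = 56 of the 97 follow-up days come after session 3. The 1-day figure also depends on a counting convention found in neither document.

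Finally, a reader might infer that the safety results would be distorted. The documents do not support this. SAP 12.2 plans per-subject proportions and raw counts, with no rate per day or per session, so no planned statistic uses exposure. Nor does Protocol 7.3.6 promise an exposure summary, so no commitment is broken.

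**Conclusion.** The point holds as a minor safety-reporting correction. SAP 12.1 states a figure that is right only for subjects with three in-window sessions, and nothing in the plan commits to reporting what was actually given. That it applies to the SAF is an inference: 12.1 names no population, but it sits under Safety Evaluation, and SAP 11.1 analyses safety in the SAF.

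The size depends on events the documents do not report. On the assumed convention and a loss of 4, the SAF mean lies between 35.2 and 42 days and total sessions between 64 and 72. Even drop-out gives 39.8 days, about 5% below 42. If all subjects receive three in-window sessions, the stated figure is correct. Adverse event incidence and the primary analysis do not change in any of these cases.

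**What to change.** Replace SAP 12.1 with text along these lines: *For the SAF, the number of sessions actually received (1, 2 or 3) will be given as N and %, with the total number of sessions given. If session dates are available, days from first to last session received (last date − first date + 1) will be summarized by N, mean, SD, median, minimum and maximum.*

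In SAP 9.1.2, state that treatment duration means actual duration, from first to last session received. Add one table to SAP 14.3, for example Table 3.3, Extent of exposure (Safety population). Reporting volume injected is optional.

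The cost is one descriptive table. Protocol 6.2.1.3 requires administration records for each subject, and Protocol 8 places study data in the eCRF. SAP 9.1 lists no session-date variable, so the availability of dates there is an assumption. This is why the day count is secondary to the session count.

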#### **12.2** Adverse Events

All enrolled subjects receiving at least one treatment injection will be included in the safety analysis.

Adverse events (AEs) and Adverse Device Events (ADEs) will be coded using the last updated version of the Medical Dictionary for Regulatory Activities (MedDRA) dictionary to give a preferred term (PT) and a system/organ class term (SOC) for each event. The number of subjects who experienced at least one AE or ADE,

CONFIDENTIAL Page 14 of 23

# STATISTICAL ANALYSIS PLAN TEMPLATE

Statistical Analysis Plan Version no. 1.0 – 20/03/2023 Clinical Investigation Plan Code FOLIAGE - 2022 EudraCT number NA

study product-related AE or ADE, serious AE or ADE, severe AE or ADE and the number of subjects withdrawn due to AE will be summarized in the Table 3.1.

For each SOC and preferred term, summaries will be made with respect to the proportion of subjects having at least one occurrence of that event during the study and the total number of events. The incidence of AEs and ADEs will be presented overall, by SOC and preferred term, and additional grouping by severity and relationship to the study treatment in the Table 3.2. Local tolerability at the site of administration will be carefully considered.

All Adverse Events will be described in the Listing 7.

#### 13. DEVIATIONS FROM THE PROTOCOL SPECIFIED ANALYSIS

Waiting for EC approval (more than 6 months, due to Ethics Committee organization and procedures) and therefore for the start of the study, the centre purchased a new corneometer (fitted with an integrated sensor - average 50), with a capacitance algorithm based on a different scale from the one assumed when drafting the protocol.

The scale of the new corneometer is based on lower numbers, with normal values around 50 rather than around 100.

Therefore, after discussions with [name], it was decided that for skin hydration at corneometer, the subjects can be considering responders to the treatment when skin hydration increase is at least 7,5 from baseline to Day 98, using an absolute evaluation, instead of a percentage as hypothesized in the protocol drafting phase.

About the inclusion criterion n. 4 "Corneometer Capacitance of the area treated  $\leq$  80", [name] declares that the capacitance = 45 at new corneometer can be consider equivalent to capacitance = 80 at previous corneometer.

No other changes from the details specified in the study protocol have been included in this Statistical Analysis Plan (SAP).

#### 14. LIST AND SAMPLES OF TABLES, FIGURES AND GRAPHS

The following lists of tables might not be exhaustive. Additional tables can be produced if necessary.

#### 14.1 Demographic data

- Table 1.1 Subjects' disposition (Safety population)
- Table 1.2 Protocol deviations (Safety population)
- Table 1.3 Demographic characteristics (Safety population)
- Table 1.4 Medical history (Safety population)
- Table 1.5 Surgical history (Safety population)
- Table 1.6 Skin and physical examination (Safety population)

CONFIDENTIAL Page 15 of 23

# STATISTICAL ANALYSIS PLAN TEMPLATE

Statistical Analysis Plan Version no. 1.0 – 20/03/2023 Clinical Investigation Plan Code FOLIAGE - 2022 EudraCT number NA

#### 14.2 Efficacy data

#### **14.2.1** Primary endpoints

Table 2.1.1 Change from baseline (Visit 1) to day 98 (Visit 4) of the skin hydration, evaluated through corneometer skin examination (FAS Population)

Table 2.1.2 Change from baseline (Visit 1) to day 98 (Visit 4) of the skin hydration, evaluated through corneometer skin examination (PP Population)

#### 14.2.2 Secondary endpoints

- Table 2.2.1 Change from baseline (Visit 1) to day 21 (Visit 2) of the skin hydration, evaluated through corneometer skin examination (FAS Population)
- Table 2.2.2 Change from baseline (Visit 1) to day 42 (Visit 3) of the skin hydration, evaluated through corneometer skin examination (FAS Population)
- Table 2.2.3 Percentage of subjects improved (Responders) on skin hydration, evaluated through corneometer skin examination, at Day 98 (Visit 4) in comparison to the baseline visit (FAS Population)
- Table 2.2.4 Percentage of subjects improved (Responders) on Investigator's Evaluation of skin texture, skin tone, smoothing of the fine lines and wrinkles at each time point (Visit 2, Visit 3 and Visit 4) in comparison to the baseline visit (FAS Population)
- Table 2.2.5 Percentage of subjects improved on the Global Aesthetic Improvement Scale (GAIS) at each time point (Visit 2, Visit 3 and Visit 4) in comparison to the baseline visit (FAS Population)
- Table 2.2.6 Percentage of subjects improved on the Patient's Aesthetic Improvement Scale (PAIS) at each time point (Visit 2, Visit 3 and Visit 4) in comparison to the baseline visit (FAS Population)
- Table 2.2.7 Subject's Evaluation of satisfaction with the treatment at Day 98 (Visit 4) by means of a 5-items scale (FAS Population)

#### 14.3 Safety data

- Table 3.1 Analysis of adverse events observed (Safety population)
- Table 3.2 Display of adverse events observed (Safety population)

#### **14.4** Sample tables

Tables reporting statistical analysis will be issued as PDF files. Mock samples are reported in the following sections.

CONFIDENTIAL Page 16 of 23

Statistical Analysis Plan Version no. 1.0 – 20/03/2023 Clinical Investigation Plan Code FOLIAGE - 2022 EudraCT number NA

## **14.4.1** Sample summary table

Sponsor: Phitogen Holding S.p.A. Page 1 of x Protocol FOLIAGE - 2022

	Table MM.M.M	
	( Popula	ation)
Characteristic	Statistic	Foliage Hydrofil
VAR 1	Class A	жж ( жж.ж%)
	Class B	ии ( ии.иф)
VAR 2	N	3030
	Mean (SD)	RR.RR (RR.RR)
	Median	NH.NH
	Min - Max	ин.ии / ин.ии
VAR 3	Class A	ин ( ин.иф)
	Class B	жж ( жж.ж∜)
	Class C	ин ( ин. и%)
	Class D	ин ( ин.иф)
VAR 4	N	MM
	Mean (SD)	MMM.MM (M.MM)
	Median	HHH. HH
	Min - Max	30300.30X / 30300.30
VAR 5	N	EK
	Mean (SD)	ин.ин (ин.ин)
	Median	RM.NH
	Min - Max	жж.жж / жжж.жж
VAR 6	N	2000
	Mean (SD)	жи.жи (ж.жж)
	Median	30.30 . 30.30
	Min - Max	ик.ик / ик.ик

Nota -

Program: Тиминии ик.sas CONFIDENTIAL Date: имXXXиини

CONFIDENTIAL Page 17 of 23

Statistical Analysis Plan Version no. 1.0 – 20/03/2023 Clinical Investigation Plan Code FOLIAGE - 2022 EudraCT number NA

# **14.4.2** Sample table for efficacy analysis – continuous variables

Sponsor: Phitogen Holding S.p.A. Page 1 of x Protocol FOLIAGE - 2022

	Table RR.R.R.R					
	(					
Endpoint	Statistic	Foliage Hydrofil				
Visit 1 (Baseline)	N	MM				
	Mean (SD)	-m.mm (m.mm)				
	Median	-x.xx				
	Min - Max	-и.ии / и.ии				
Visit 2	N	жж				
	Mean (SD)	- m . mm ( m . mm)				
	Median	-16.1636				
	Min - Max	-и.ии / и.ии				
	p-value	x.xxx				
Visit 3	N	жж				
	Mean (SD)	- m . mm ( m . mm)				
	Median	-36.3636				
	Min - Max	-ж.жж / ж.жж				
	p-value	n.nn				
Visit 4 (End of study)	N	ких				
	Mean (SD)	-x.xx (x.xx)				
	Median	-x.xx				
	Min - Max	-н.нк / н.нк				
	p-value	и. иии				

Statistical significance: \* p<0.05

Program: Тимимими мим.sas CONFIDENTIAL Date: миXXXимими

CONFIDENTIAL Page 18 of 23

Statistical Analysis Plan Version no. 1.0 – 20/03/2023 Clinical Investigation Plan Code FOLIAGE - 2022 EudraCT number NA

# **14.4.3** Sample table for efficacy analysis – discrete variables

Sponsor: Phitogen Holding S.p.A. Page 1 of x Protocol FOLIAGE - 2022

	Table xx.x.x. (				
Characteristic	Statistic	Foliage Hydrofil			
Visit 1 (Baseline)	Class A	ин ( ин.и\$)			
	Class B	ии ( ии.и\$)			
Visit 2	Class A	ин ( ин.и\$)			
	Class B	жи ( жи.и\$)			
	p-value	M.HHH			
Visit 3	Class A	ин ( ин.н4)			
	Class B	ик ( ик.и\$)			
	p-value	x.xxx			
Visit 4 (End of study)	Class A	ии ( ии.и\$)			
	Class B	жж ( жж.ж%)			
	p-value	36 . 363636			

Statistical significance: \* p<0.05

Frogram: Тимининин ини.sas CONFIDENTIAL Date: инXXXинин

CONFIDENTIAL Page 19 of 23

Statistical Analysis Plan Version no. 1.0 – 20/03/2023 Clinical Investigation Plan Code FOLIAGE - 2022 EudraCT number NA

## **14.4.4** Sample table for adverse events analysis

Sponsor: Phitogen Holding S.p.A. Page 1 of x Protocol FOLIAGE - 2022

Table xx.x.x.x Analysis of adverse events observed (Safety Population)

AE details	Statistic	Foliage Hydrofil			
Have any AE occurred?	NO	и (ин.и\$)			
	YES	n ( nn.n%)			
Total number of adverse events	N	(N=36363)			
Relatedness with study treatment	Certain	ж (жж.ж\$)			
	Probable	и (ии.и*)			
	Possible	и (ин.и*)			
	Doubtful	и (ии.и\$)			
	None	м (мм.мф)			
	Unknown				
Severity	Grade 1 (Mild)	n ( nn.n\$)			
	Grade 2 (Moderate)	и (ик.и\$)			
	Grade 3 (Severe)	и (ии.и\$)			
	Grade 4 (Life-threatening consequences)				
	Grade 5				
Seriousness	YES	n ( nn.nt)			
	NO	n ( nn.n%)			

Statistical significance: \* p<0.05

Frogram: THINDUNDUNG HIM. SAS CONFIDENTIAL Date: HINDUNDUNG

CONFIDENTIAL Page 20 of 23

Statistical Analysis Plan Version no. 1.0 – 20/03/2023 Clinical Investigation Plan Code FOLIAGE - 2022 EudraCT number NA

## **14.4.5** Sample table for adverse events display

Sponsor: Phitogen Holding S.p.A. Protocol FOLIAGE - 2022 Page 1 of x

Table xx.x.x.x Display of adverse events observed (Safety Population)

		Foliage Hydrofil						
-	Organ Class (SOC) Preferred Term (PT)	Event	Patients	(%)				
OVERALL	Preferred Term (PI)			x.xx				
SOC 1		x	x	x.xx x.xx				
	T 1	×	x	x.xx				
	T 2	×	x	x.xx				
	r 2 r 3	x	x	x.xx				
. P	1 3	x	x					
SOC 1		x	x	x.xx				
. P	T 1	x	x	x.xx				
. P	T 2	x	x	x.xx				
	г 3	×	x	x.xx				
SOC 1		x	x	x.xx				
. P	T 1	×	x	x.xx				
	T 2	x	x	x.xx				
. P	Т 3	×	x	x.xx				
SOC 1		×	x	x.xx				
. P	T 1	x	x	x.xx				
	T 2	x	x	x.xx				
	Г 3	×	x	x.xx				
SOC 1		x	x	x.xx				
	T 1	×	x	x.xx				
	T 2	x	x	x.xx				
	Г 3	×	x	x.xx				
SOC 1		x	x	x.xx				
	T 1	x	x	x.xx				
	T 2			x.xx				
	I 3	x	x	x.xx				
	• •	×	x					
SOC 1		x	x	x.xx				
	T 1	x	x	x.xx				
	T 2	x	x	x.xx				
. P	Т 3	x	x	x.xx				

Program: Thindhddin hin.sas CONFIDENTIAL Date: hin/DONadin

CONFIDENTIAL Page 21 of 23

Latis Srl

Vers. No. 03, 05/02/18 (Ref. SOP No. 16)

# STATISTICAL ANALYSIS PLAN TEMPLATE

Statistical Analysis Plan Version no. 1.0 – 20/03/2023 Clinical Investigation Plan Code FOLIAGE - 2022 EudraCT number NA

#### 15. REFERENCES

None.

#### 16. APPENDICES

#### **16.1** Study information

Study information appendices will be attached to the CIR.

#### 16.2 List and samples of Subject Data Listings

The following list of listings might not be exhaustive. Additional listings can be produced if necessary.

The following data listings will be attached to the CIR:

Listing 1 Discontinued subjects

Listing 2 Protocol deviations

Listing 3 Subjects excluded from the efficacy analysis

Listing 4.1 Demographic data

Listing 4.2 Medical history

Listing 4.3 Surgical history

Listing 4.4 Skin and physical examination

Listing 5.1 Individual efficacy response data – skin hydration at each time point (Visit 1, Visit 2, Visit 3 and Visit 4)

Listing 5.2 Individual efficacy response data – skin surface characteristics at each time point (Visit 1, Visit 2, Visit 3 and Visit 4)

Listing 5.3 Individual efficacy response data – Global Aesthetic Improvement Scale (GAIS) by the investigator at each time point (Visit 2, Visit 3 and Visit 4)

Listing 5.4 Individual efficacy response data – Patient's Aesthetic Improvement Scale (PAIS) at each time point (Visit 2, Visit 3 and Visit 4)

Listing 5.5 Individual efficacy response data – subject overall satisfaction at Day 98 (Visit 4)

Listing 6 Adverse events

Listing 7 Concomitant medications

CONFIDENTIAL Page 22 of 23

Statistical Analysis Plan Version no. 1.0 – 20/03/2023 Clinical Investigation Plan Code FOLIAGE - 2022 EudraCT number NA

